5.4. Lifestyle Restrictions

5.4.1. Dietary Restrictions

Foods such as star fruit juice, Seville orange juice, and grapefruit juice that are strong to moderate inhibitors of P450 (CYP) 3A4 should be avoided.

Study drug can be taken with or without food.

5.4.2. Highly Effective Contraception

Highly effective methods of birth control are defined as those which result in a low failure rate (i.e., less than 1% per year) when used consistently and correctly.

For female patients - WOCBP:

- Combined (estrogen and progestogen containing) hormonal contraception associated with inhibition of ovulation:
 - Oral
 - Intravaginal
 - Transdermal
- Progestogen-only hormonal contraception associated with inhibition of ovulation:
 - Oral
 - Injectable
 - Implantable

Note: Hormonal contraception must be supplemented with another form of contraception that may include but is not limited to another form of highly effective contraception (e.g., IUD) or other barrier methods (such as male condom plus spermicide or female diaphragm).

- Intrauterine device (IUD)
- Intrauterine hormone-releasing system (IUS)
- Bilateral tubal ligation
- Vasectomized partner. Note that a vasectomized partner is a highly effective birth control method provided that partner is the sole sexual partner of the woman of childbearing potential trial patient and that the vasectomized partner has received medical assessment of the surgical success.
- Sexual abstinence. Sexual abstinence is considered a highly effective method only if the subject is refraining from heterosexual intercourse during the entire period of risk associated with the study treatments. The reliability of sexual abstinence needs to be evaluated in relation to the duration of the clinical trial and the preferred and usual lifestyle of the subject.
- Same sex partner

Women who have not menstruated for at least 12 months and with follicle-stimulating hormone (FSH) levels ≥ 30 mIU/mL will be considered postmenopausal and will not be required to use contraception.

For male patients with a partner of childbearing potential:

Men must agree to use two acceptable methods of contraception (e.g., condom plus spermicide), at least one of which must be a barrier method for the entire duration of the study, and for 3 months following last study drug administration.

6. STUDY DRUGS AND CONCOMITANT THERAPY

6.4. Study Drug Accountability

The Investigator or his/her designated representatives will dispense study drug per the Schedule of Assessments (see [Section 1.3](#)).

The Investigator is responsible for the control of drugs under investigation. Adequate records of the receipt (e.g., Drug Receipt Record) and disposition (e.g., Investigation Drug Dispensing Log) of the study drug must be maintained. The Investigation Drug Dispensing Log must be kept current and should contain the following information:

- The identification (ID) of the patient to whom the study drug was dispensed (that is, patient ID number and year of birth)
- The date(s), quantity, and lot number(s) of the study drug dispensed to the patient
- The ID of the person who dispensed the study drug

All used and unused drug supplies must be returned by the patient at every visit.

All records and used and unused drug supplies must be available for inspection by the study monitor at every monitoring visit. Reconciliation of all drug supplies (ESK-001 or placebo) will be performed by the study monitor.

6.5. Destruction of Study Drug

When the study is completed, the Investigator will destroy or return to the Sponsor any used and unused study drug (e.g., empty, partially used, and unused containers), to the Sponsor as requested. Copies of the completed Drug Dispensing Log and Drug Return Record(s) will be returned to the Sponsor. The Investigator's copy of the Drug Return Record(s) must accurately document the return or destruction of all drug supplies to the Sponsor.

Local or institutional regulations may require immediate destruction of used study drug for safety reasons. In these cases, it may be acceptable for investigational study center staff to destroy dispensed study drug before a monitoring inspection, provided that source document verification is performed on the remaining inventory and reconciled against the documentation of quantity shipped, dispensed, returned, and destroyed, and provided that adequate storage and integrity of drug has been confirmed. Written authorization must be obtained from the Sponsor or Sponsor designees after final accountability prior to destruction.

Unused study drug from the site that has not been stored properly should not be destroyed until the monitor and/or Sponsor approve the destruction.

Written documentation of destruction must contain the following:

- Identity of study drug destroyed
- Quantity of study drug destroyed
- Date of destruction
- Method of destruction
- Name and signature of responsible person who destroyed the study drug

6.6. Patient Identification and Randomization Procedure

All screened patients are assigned unique identification number. Screened patients who drop out of the clinical study before randomization will retain their unique identification number.

Blister card wallets will provide blinded serial numbers for allocation using randomization through an interactive voice/web response system (IxRS) or equivalent process of distribution of the study drug throughout the duration of the study. Patients will be randomized 1:1:1:1:1:1 one of the 6 treatment arms (5 dose levels of ESK-001, placebo).

Randomization will be stratified by prior use of biologics and geographic region. A permuted block randomization scheme will be used to obtain approximately a 1:1:1:1:1:1 ratio among the treatment arms within each stratum.

6.7. Blinding and Emergency Unblinding

ESK-001 tablets and placebo-to-match ESK-001 tablets will be matched for shape, size and color.

Study drug assignment for each patient will not be disclosed to the Investigator, study center personnel, patients, or the Sponsor or representatives on the clinical study team. Study site personnel will remain blinded throughout the entirety of the study.

If at any time during the study a decision about a patient's medical condition requires knowledge of the treatment assignment, the study blind may be broken by the Principal Investigator, (through the IxRS), for that specific patient only. If in the opinion of the Investigator, there is no impact on patient safety, the Investigator is strongly encouraged to contact the Sponsor's Medical Monitor prior to unblinding. The reason for unblinding must be documented in the IxRS or appropriate study documentation.

At the study site, only the Principal Investigator should be unblinded. If, in the Investigator's opinion, and for the safety of the patient other study site personnel are required to be aware of the treatment assignment, the Investigator will contact the Sponsor's Medical Monitor prior to further unblinding and ensure that the minimum number of personnel are informed.

The SMC must be informed by the Sponsor's Medical Monitor of any case of unblinding. Additionally, the SMC may unblind individual treatment assignment for further safety evaluation at their discretion.

6.8. Administration of Study Drug

The study site staff will administer a dose of study drug to each patient on Day 1 (first dose), and on the Week 4, 8, and 12 visit days. Patients should be clearly instructed not to take study drug on these study Days, but to bring their study drug with them to the clinic and take [REDACTED]

Study drug will be dispensed to patients as a 4-week supply at the Day 1, Week 4, and Week 8 visits.

At the Week 4, 8 and 12 study visits patients must return all study drug [REDACTED]

6.9. Continued Access to Investigational Product

After completion of the Week 16 End-of-Study (EOS) Visit, Patients will be eligible to receive extended open-label treatment with ESK-001 by participating in a separate open-label extension (OLE) study (Protocol No. ESK-001-007). To participate in this OLE study patients must have

completed this study, ESK-001-006, meet all eligibility criteria for the OLE study, and be willing and able to complete all of its required assessments.

6.10. Treatment of Overdose

Standard symptomatic support measures should be used in the case of excessive pharmacological effects or overdose. No antidotes are available.

6.11. Treatment Compliance

Accountability and patient compliance will be assessed by maintaining adequate study drug dispensing records and tablet counts. The Investigator is responsible for ensuring that dosing is administered in compliance with the protocol. See [Section 6.4](#) for instructions on drug accountability procedures.

6.12. Prior and Concomitant Medication

Prior and concomitant medication as well as vaccination use after screening will be recorded on the prior and concomitant eCRF. Prior medications should be collected from the past 10 years.

Antiviral Medications

Based on in vitro assessments, ESK-001 has the potential for drug-drug interaction with antiviral medications metabolized through CYP3A4, CYP2D6 and P-gp pathways (eg, Paxlovid [nirmatrelvir + ritonavir]). Co-administration with ESK-001 may affect the systemic exposure levels of antiviral medications or ESK-001. The benefit:risk assessment for administration of anti-viral medications with a narrow therapeutic index should be discussed with the medical monitor whenever possible.

Acid Reducing Agents

The use of Proton Pump Inhibitors (PPIs) are not permitted on study due to the potential to decrease ESK-001 exposure. However, the use of H2 blockers (e.g., famotidine or ranitidine) and calcium carbonate-containing antacids (eg, Tums® or Rolaids®) are allowed during the study but should be taken at least 2 hours after a dose of study drug.

6.12.1. Allowed Vaccinations

Inactivated vaccines (including but not limited to COVID-19 vaccines and boosters) will be allowed while on study. The study site should follow local guidelines related to COVID-19.

6.12.2. Prohibited Medications

Medication and treatment restrictions applicable before the dosing period are listed as exclusion criteria in [Section 5.3](#). These restrictions are applicable for the duration of the study and are summarized in [Table 2](#). Prior and concomitant medication will be recorded.

Table 2 Prohibited Treatments

Treatment Category	Examples ^A	Washout Period ^B
Topical medications or treatments that could affect psoriasis evaluation	corticosteroids, anthralin, calcipotriene, vitamin D derivatives, retinoids	2 weeks
Phototherapy or systemic medications or treatments that could affect psoriasis evaluation	oral or injectable corticosteroids, retinoids, 1,25-dihydroxy vitamin D3	4 weeks
Therapeutic agents targeted to IL-12 or IL-23	ustekinumab, guselkumab, tildrakizumab, risankizumab	6 months
Therapeutic agents targeted to IL-17	secukinumab, ixekizumab, brodalumab	4 months
TNF α inhibitors	etanercept, infliximab, adalimumab	2 months
Systemic immunosuppressants or immunomodulatory drugs	corticosteroids (oral/IV/IM/SC), methotrexate, azathioprine, cyclosporine, mycophenolate mofetil	4 weeks or 5 half-lives ^C
Agents that modulate B cells	rituximab, ocrelizumab	6 months
Agents that modulate T cells	abatacept, alemtuzumab	3 months
JAK inhibitors or TYK2 inhibitors	baricitinib, tofacitinib, upadacitinib, ruxolitinib, fedratinib, deucravacitinib	4 weeks
Investigational agents		30 days or 5 half-lives ^C
Proton pump inhibitors	omeperazole, esomeprazole, pantoprazole	Prior to Study Day 1

- A. Including but not limited to
- B. Prior to randomization on Study Day 1
- C. Whichever is longer

7. DISCONTINUATION

7.1. Discontinuation of the Study or Site

The Sponsor has the right to terminate this study at any time. Reasons for terminating the study may include, but are not limited to:

- Incidence or severity of adverse events in this or other studies indicating a potential safety risk to patients.
- Unsatisfactory patient recruitment e.g., excessively slow
- Poor protocol adherence
- Incomplete or inaccurate data recording
- Poor compliance with the International Conference on Harmonisation (ICH) guidelines for Good Clinical Practice (GCP)

In any instance of early discontinuation of the study, the Sponsor will notify, in writing, the investigators, regulatory authorities and ethics committees, and will specify the reason(s) for termination.

7.2. Study Drug Discontinuation

Patients should discontinue study drug for any of the following reasons:

- Malignancy, not including local and non-serious basal, squamous cell skin cancer or ductal carcinoma in situ
- Pregnancy
- Anaphylaxis, anaphylactoid or serious hypersensitivity reaction
- Use of any medication, intended to chronically treat psoriasis (refer to [Section 6.12.2](#)), other than those documented at screening
- Adverse event which in the opinion of the investigator or SMC precludes the patient from safely continuing in the study
- Patient is noncompliant with study requirements

The date and reason for discontinuation should be documented in the eCRF.

Patients who discontinue study drug should continue in the study to complete all scheduled assessments.

Those patients who are unwilling or unable to complete all remaining study assessments should return to the study site 2 weeks (\pm 7 days) after the date study drug was discontinued, to complete the early study termination assessments (ET Visit).

7.3. Discontinuation of Individual Patients

Reasons for patient discontinuation from the study may include but are not limited to any of the following reasons:

- Patient withdrawal of consent
- Discretion of the Investigator, if it is deemed not safe, or in the patient's best interest, to continue
- SMC recommendation
- Patient is lost to follow-up

The date and reason for discontinuation should be documented in the eCRF.

Patients who discontinue the study should return to the site to complete the early study termination assessments (ET Visit) within 2 weeks (\pm 7 days) from the date of discontinuation.

If a patient discontinues the study without notifying the Investigator, every effort should be made to contact the patient to identify the reason for discontinuation and to encourage the patient to complete the applicable ET visit assessments. If documented attempts to contact the patient fail, and a reason for the patient's discontinuation is undiscoverable, a patient can be declared as "lost to follow up" at the end of the study. All efforts to contact the patient should be documented in the source documents.

8. STUDY ASSESSMENTS AND PROCEDURES

For timing of assessments, refer to the Schedule of Assessments (SOA) in [Section 1.3](#).

8.1. Eligibility Screening

Informed consent will be obtained at Screening before performing any study procedures.

Patients will undergo Screening assessments, including, but not limited to blood sampling, ECG, clinical assessment and various QoL assessments. Patients may be rescreened once no sooner than 2 weeks after an initial screen failure after discussion with the medical monitor.

Medical and medication history as well as demographic data, including biological sex, age, race, body weight (kg) and height (cm) will be recorded.

8.2. Efficacy Assessments

8.2.1. Psoriasis Area and Severity Index

Disease activity will be assessed by the Psoriasis Area and Severity Index (PASI) at the timepoints indicated in the Schedule of Assessments (see [Section 1.3](#)). The PASI system derives a score for the severity of psoriatic lesions by evaluating erythema, induration, and scaling in each of 4 body regions, as detailed in [Appendix A](#). The primary and secondary endpoints are based on the PASI response at the end of treatment (12-week timepoint).

8.2.2. Psoriasis Body Surface Area

Measurement of psoriasis body surface area (BSA) involvement is estimated using the handprint method with the size of a patient's handprint representing ~1% of body surface area involved. The total BSA = 100% with breakdown by body region as follows: head and neck = 10% (10 handprints), upper extremities = 20% (20 handprints), trunk including axillae and groin = 30% (30 handprints), lower extremities including buttocks = 40% (40 handprints). BSA assessments should be performed by a dermatologist or appropriately trained investigator who is experienced in the assessment of psoriasis patients.

8.2.3. Physician's Global Assessment

Patients will be assessed by the static Physician's Global Assessment (sPGA) at the timepoints indicated in the Schedule of Assessments (see [Section 1.3](#)). [Appendix B](#) presents the scoring system used for the sPGA.

8.2.4. Patient-Reported Outcomes

Quality of life (QoL) will be assessed by patient-reported outcomes: the Dermatology Life Quality Index (DLQI), the EQ-5D, and the pruritus numerical rating scale (NRS) at the timepoints indicated in the Schedule of Assessments (see [Section 1.3](#)). The 10-question DLQI is presented in [Appendix C](#), the 5-question EQ-5D-5L is shown in [Appendix D](#), and the pruritus NRS is presented in [Appendix E](#).

8.3. Safety Assessments

ESK-001 is not an approved drug and as a result the entire safety profile is not known at this time. This Phase 2 study will contribute to the understanding of the safety profile for ESK-001 and for its use in patients with moderate to severe psoriasis.

Safety assessments will consist of recording all AEs and SAEs, protocol-specified laboratory variables, vital signs, and the results from other protocol-specified tests that are deemed critical to the safety evaluation of ESK-001. Dedicated eCRFs will be used to collect information on specific AEs, including SAEs, and pregnancies.

8.3.1. Adverse Events

An AE is defined as any untoward medical occurrence in any study participant enrolled in a clinical investigation administered a pharmaceutical product regardless of causal attribution.

An AE can therefore be any unfavorable and unintended sign (including an abnormal laboratory finding), symptom, or disease temporally associated with the use of an investigational product, whether or not it is thought to be related to the investigational product.

In addition to new events, any increase in the severity or frequency of a pre-existing condition that occurs is considered an AE.

Only clinically significant laboratory test abnormalities (in the medical opinion of the Investigator) that require active management (e.g., abnormalities that require study drug discontinuation, more frequent follow-up assessments, further diagnostic investigation, etc.) should be listed as AEs. See [Section 8.3.1.3](#) for more details.

If the AE constitutes a disease or syndrome (e.g., upper respiratory tract infection), only the diagnosis (e.g., upper respiratory tract infection) should be recorded as an AE and not the individual symptoms (fever, headaches, body aches, runny nose, sore throat, etc.). If an AE is due to an inactivated vaccine, the AE together with the etiology should clearly be recorded.

Other untoward events occurring in the framework of a clinical study will be recorded as AEs, e.g., those occurring during treatment-free periods (including Screening or post-treatment follow-up periods) in association with study-related procedures and assessments, or under placebo. For study drugs, lack of efficacy may be an expected potential outcome and should not be reported as an AE unless the event is unusual in some way, e.g., greater in severity.

Concomitant illnesses: Medical conditions which existed prior to entry into the clinical study will not be considered AEs unless they worsen (frequency or severity) during the treatment period. Pre-existing conditions will be recorded as part of the participant's medical history. Day to day fluctuations of pre-existing disease should not be recorded as an AE on the AE eCRF.

Disease under study (psoriasis): Disease related progression and worsening signs or symptoms of the disease under study are not AEs and are not to be recorded on the AE page of the eCRF unless the event meets the definition of an SAE or is not consistent with the typical clinical course of the patient's disease as established by the patient's medical history.

Surgical or diagnostic procedures: For medical or surgical procedures (e.g., colonoscopy, biopsy), the medical condition that led to the procedure is an AE. Elective procedures (e.g.,

vasectomy), planned hospitalization, and procedures for treatment of conditions noted in the patient's medical history that have not worsened (e.g., hernia repair) are not considered AEs.

All reported AEs will be coded using the Medical Dictionary for Regulatory Activities (MedDRA).

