4.4. Study Duration

The estimated study duration for each patient is approximately 20 weeks and includes:

1. The screening period: up to 4 weeks
2. Treatment period: 12 weeks
3. Safety follow-up period: 4 weeks

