8.3.1.1. Recording of Adverse Events

Adverse events should be collected and recorded for each patient from the date of the first screening/eligibility assessment until the end of their participation in the study, i.e., the patient has discontinued or completed the study.

Reporting of AEs prior to first dose should only include SAEs or AEs resulting from any protocol-related interventions.

Adverse events are to be recorded on the AE page of the eCRF. The following information will be recorded at the time the AE is reported and during follow up during the course of the AE:

- Whether or not the AE is an SAE (see [Section 8.3.1.2.1](#))
- AE severity using CTCAE criteria (see [Section 8.3.1.2.2](#))
- AE relationship to study drug (see [Section 8.3.1.2.3](#))
- Action taken; including but not limited to, none, study drug dose modification or discontinuation, required concomitant medication, required procedure, or other
- Outcome: recorded as event resolved, resolved with sequelae, ongoing, or death

If an adverse event is persistent i.e. continues between various study assessment timepoints without resolution it should be recorded only once (see [Section 8.3.1.3](#)).

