8.3.1.4. Reporting of SAEs

Any AE that is serious and that occurs during the course of the study from the signing of the informed consent to end of study for each patient must be reported by the Investigator to the following:

- The Sponsor (or designee) and study monitor within 24 hours of the Investigator becoming aware of the event (expedited reporting).
- The investigation site's IRB/IEC by the Investigator in accordance with their regulations.

Initial Notification of a Serious Adverse Event (SAE)

Pharmacovigilance must be informed in writing 24 hours from the time the site investigational team first becomes aware of the event using the EDC system, as well as completing a paper SAE report forms.

A paper SAE form including a written, narrative description of any SAE must be sent via email (preferred) or fax within 24 hours after awareness of the event to:

Email: [REDACTED]

Phone: [REDACTED]

Fax: [REDACTED]

Paper SAE forms must be retained in the Investigator Site File.

In addition to reporting the SAE in the EDC and emailing the paper form, the local CRA and the Medical Monitor must be alerted via phone.

As further information regarding the SAE becomes available, follow-up information should be documented as an update using the paper SAE form. Follow-up information should be reported with 24 hours of awareness.

Related SAEs must be collected and reported regardless of the time elapsed from the last administration of study drug, even if the study has been closed.

Unrelated SAEs must be collected and reported during the study and for up to 30 days after the last dose of study medication.

SUSARs are reported to Investigators at each site and associated IRB/IEC when the following conditions occur:

- The event is an SAE
- There is reasonable possibility that the event is an adverse reaction caused by the administered drug
- The adverse reaction is unexpected, that is to say, not foreseen in the IB

Individual SUSARs considered to be a significant safety issues and/or which result in a change to the informed consent form will be reported in an expedited manner to all Investigators and IRB/IECs.

Reporting of any SAEs to applicable regulatory authorities will be the responsibility of the Local Sponsor in compliance with local regulations.

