8 SAFETY ANALYSES

All safety analyses will be performed on the Safety Analysis Population and will be presented by each treatment group and the combined active treatment. In general safety data will be presented by descriptive statistics only and by nominal visit (if applicable). Safety data collected on unscheduled visits will be presented in listings only.

The treatment emergent period is defined as first dose through the end of study for subjects who complete the full treatment period of 12 weeks. If a subject discontinues study drug early, then the treatment emergent period will be first dose through four weeks after last dose.

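### Protocol Section 8.3.1 gives two conflicting rules on whether a pre-existing condition that worsens in the 4-week safety follow-up is an adverse event

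*Protocol*

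**What the plan says.** Protocol Section 8.3.1 (Adverse Events) deals with pre-existing conditions twice. Near the start it says that, besides new events, "any increase in the severity or frequency of a pre-existing condition that occurs is considered an AE". The later paragraph on concomitant illnesses says that conditions present before entry "will not be considered AEs unless they worsen (frequency or severity) during the treatment period".

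The provisions that bear on which rule applies after Week 12 are:

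- **Protocol Section 4.4** lists "Treatment period: 12 weeks" and, as a separate item, a safety follow-up of 4 weeks. The Schedule of Assessments (Section 1.3) puts Weeks 14 and 16 under their own follow-up heading, with AE review at both visits.
- **Protocol Section 8.3.1.1** collects AEs from the first screening assessment "until the end of their participation in the study, i.e., the patient has discontinued or completed the study". Before first dose, it limits reporting to SAEs and to AEs that result from protocol-related interventions.
- **Protocol Section 8.3.1.4** requires any serious AE "from the signing of the informed consent to end of study for each patient must be reported".
- **SAP Section 8**: "The treatment emergent period is defined as first dose through the end of study" for patients who complete 12 weeks of treatment. For patients who stop study drug early, the period ends four weeks after last dose.

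**The concern.** The SAP's treatment-emergent period deliberately includes time after the last dose. For pre-existing disease, one protocol sentence tells sites that worsening in that time is not an AE. A coordinator deciding how to handle a known comorbidity would naturally turn to the paragraph headed for that case, which is the restrictive one. Another site could follow the general sentence with equal justification.

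The incidence of TEAEs and SAEs is a secondary endpoint, and Protocol Section 8.3 acknowledges that the full safety profile is not yet known. Relevant comorbidity is expected. Section 5.3 admits patients with psoriatic arthritis on a stable regimen without immunosuppressants, stable treated cardiovascular disease, asthma on stable inhaled corticosteroids, and psychiatric illness on a fixed regimen. SAP Section 5.2 lists comorbidity as a possible subgroup. An event that a site never enters on the AE page cannot be restored to the AE tables at analysis.

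**Working it through.** The plan states no figure to reproduce here. The check compares the texts and then measures the period over which they conflict.

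**Step 1. Does the treatment period include follow-up?** Section 4.4 gives screening of up to 4 weeks, treatment of 12 and follow-up of 4. The sum is 4 + 12 + 4 = 20 weeks, which matches the stated duration of approximately 20 weeks. The total works only if follow-up is additional to the treatment period. The restrictive sentence, read as written, therefore stops at Week 12.

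**Step 2. The rules side by side, for a comorbidity that worsens at Week 14 in a patient who completed treatment.**

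| Provision | Result |
|---|---|
| 8.3.1, general sentence | AE |
| 8.3.1, concomitant illnesses | Not an AE |
| 8.3.1.1, collection period | Still open |
| SAP Section 8, treatment-emergent period | Still open |

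**Step 3. Do other provisions settle the conflict?** Not clearly.

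- Section 8.3.1.1 says when AEs are collected, whereas the disputed sentence says what counts as one. A collection period that is still open does not capture an event defined as not an AE.
- Section 8.3.1 also records events outside treatment, but its examples are "those occurring during treatment-free periods (including Screening or post-treatment follow-up periods) in association with study-related procedures and assessments, or under placebo". Spontaneous worsening of a comorbidity in follow-up is not clearly among them.
- Section 8.3.1.2.1 defines an SAE as an AE with a listed outcome, and Section 8.3.1.4 covers AEs that are serious. If the worsening is not an AE, the SAE rules do not clearly reach it. The psoriasis paragraph has an explicit exception for events that meet the SAE definition; the concomitant-illness paragraph has none.

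**Step 4. Length of the conflict, for a patient who completes treatment.**

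- In nominal weeks, the treatment-emergent period is 12 + 4 = 16 weeks and the disputed part is 4/16 = 25%.
- By Schedule of Assessments days (Week 12 at Day 84, Week 16 at Day 115), it is (115 − 84)/115 = 31/115 = 27%.
- By SAP Appendix B target days (85 and 113), it is (113 − 85)/113 = 28/113 = 25%.

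**Step 5. Patients who stop study drug early.** The size depends on a reading that the protocol does not fix. Take a last dose at Week 8 as an illustration, so that the SAP window is 8 + 4 = 12 weeks. If the treatment period ends with the patient's last dose, 4/12 = 33% of the window is in dispute. If it means the scheduled 12 weeks, the window closes at Week 12 and none is.

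**The case against.** The strongest reply is that most of the protocol points towards recording. The general sentence has no time limit, collection runs to the end of participation, and AE review is scheduled at Weeks 14 and 16. The test in Section 8.3.1 for procedures on medical-history conditions asks only whether the condition has worsened, not when. On this view, one loose phrase stands against several contrary instructions.

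This stands against the reading a reader might draw from the restrictive sentence alone, that follow-up worsening of pre-existing conditions is not recorded. The documents support only a contradiction, with recording that may vary. Nothing suggests that the sponsor chose to exclude such events. It does not remove the contradiction, because none of these provisions says which sentence prevails.

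Two further replies have some force. First, safety data are not confined to the AE page. Vital signs are taken at Weeks 14 and 16, laboratory tests and ECG at Week 16, and the SAP summarises these whether or not an AE is entered. Worsening blood pressure could show there. Concomitant medication is also captured through end of study (SAP Section 6.5). This softens the effect for measurable conditions, less so for arthritis, asthma or psychiatric illness, and it does not correct AE incidence. Second, Protocol Section 11.4.2 refers to CRF completion guidelines, which are not among the documents and might already resolve the point. Variation between sites is therefore a risk and has not been shown.

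**Conclusion.** Section 8.3.1 contradicts itself on worsening of pre-existing conditions during safety follow-up. Its restrictive sentence also conflicts with Section 8.3.1.1 and with the SAP's treatment-emergent period. Where a site follows that sentence, it can only remove entries, so TEAEs and possibly SAEs may be under-counted. The effect on comparisons between arms is unknown, and the primary endpoint is untouched.

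For completers the conflict covers about 4 of 16 weeks. A reader might take the 25% as a share of AEs lost. It is not: the documents give no rate of worsening for comorbidities and no information on which sentence sites follow, so the loss cannot be computed. A reader might also suppose that the SAP counts every patient to end of study. It does so only for patients who complete 12 weeks of treatment. Patients who stop early are asked to stay for all scheduled assessments (Protocol Section 7.2), so their participation can run past their treatment-emergent period. Worsening of psoriasis is outside this point because Section 8.3.1 gives it a separate rule.

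The conclusion rests on reading the treatment period as Section 4.4 and the Schedule of Assessments define it.

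**What to change.** In the concomitant-illness sentence of Protocol Section 8.3.1, replace the limit to the treatment period with: *during the AE collection period defined in Section 8.3.1.1*. That period runs to the end of participation and keeps the pre-dose limit to SAEs and AEs from protocol-related interventions. A wording that started at first dose would fit less well, because it would leave out the pre-dose events that Section 8.3.1.1 retains.

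The SAP needs no change. Sites record the event, and the SAP applies its treatment-emergent window at analysis, including the earlier cut-off for patients who stop study drug early. A matching line in the CRF completion guidelines would help sites apply the rule in the same way.

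The cost is one phrase in a protocol amendment, with the ethics approval that Section 11.2 requires for any amendment, and a few more AE entries. If follow-up is already complete, the clinical study report should state which rule sites applied.
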